#### **8.2.6. Initial 24 Month Treatment Intervention Early Termination (+ 2 weeks)**

Within 2 weeks off final study pill treatment for any cause, all subjects will have a follow-up history and physical exam/review of body systems (including, weight and vital signs), along with toxicity assessment. Repeat blood laboratory tests (CBC, chemistry panel, and urinalysis), a random urine sample will be obtained for polyamine determination, EKG (Subject needs to be in the supine position for 10 minutes prior to the EKG) and audiometry will be performed. Women

of child bearing potential will also have a serum pregnancy test performed. Concomitant medications, adverse events and medication compliance will also be reviewed. Quality of life questionnaires (EORTC QLQ-C30, EORTC QLQ-CR29, EQ-5D and the modified Cancer Worry Scale) will be provided to the subject to complete. A food frequency questionnaire will be provided to the subject to complete at North American (United States and Canada) sites only.

Repeat upper and lower endoscopies with image and video documentation will be obtained at the Month 24/EOT visit or if the subject has completed at least 3 months of treatment from the previous on-study upper and lower endoscopy procedures (including baseline). A normal mucosal biopsy sample for polyamine determination will be obtained during the colonoscopy/proctoscopy procedure.

If the subject has an unscheduled upper/lower endoscopy for any reason, these procedures should be captured with image and video documentation including the collection of a normal mucosal biopsy, if possible. A random urine sample should be obtained for polyamine determination, if possible.

Subjects will be formally taken off-study treatment and complete the End of Treatment (EOT) assessments if there is a cumulative delay/suspension of study medication for any reason of:

- > 90 days from randomization to month 36
- > 105 days from randomization to month 42
- > 120 days from randomization to month 48

A temporary suspension from taking study medication as stated above (for example, due to a non-FAP disease related surgery or procedure), will be documented as a treatment delay and the subject will continue on study, on their original schedule.

#### **8.2.7. Initial 24 Month Treatment Intervention Follow-Up (30-days post end of treatment visit +/- 1 week) Off Study**

Thirty-days (30) after completion of the end of study evaluations, subjects will be contacted by phone for a clinical update in regard to symptoms and interval medical history. Concomitant medications and adverse events will also be reviewed. The subject will provide a clinical update and procedure date for any FAP-related surgical event or major endoscopic excisional event that has occurred since the last contact. These include partial colectomy, colectomy with IRA, total procto-colectomy, proctectomy, pouch resection, sub-mucosal resection, trans-duodenal excision, ampullectomy, duodenectomy, or Whipple procedure.

An FAP-related event at any disease site (colon/rectum/pouch, duodenum) will lead to discontinuation of the study treatment but follow-up of the subject will continue until the end of the 30 day follow-up period.

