Recently, a clinical trial of eflornithine in combination with another NSAID for prevention of polyps in FAP patients has been reported. Lynch *et al.* [ENREF 26](#) have reported results of a trial using 500 mg/m^2/day eflornithine, rounded to the nearest 250 mg as 250 mg tablets were used in this study, combined with 400 mg BID celecoxib. After correcting for body surface area, the average eflornithine dosage was three (3) 250 mg eflornithine tablets PO daily. While the effect of the combination was not different from celecoxib alone for the primary endpoint (duodenal and colorectal polyp number), the Lynch *et al.* study provided evidence for effectiveness of the combination versus celecoxib alone (statistically significant reductions in the secondary endpoints of polyp volume and global polyp burden). No differences in toxicities, including ototoxicities, were observed between treatment arms in this study. Another study in non-FAP patients but relevant to potential safety issues of the higher eflornithine dose has also been reported. Bailey and colleagues treated 291 patients with prior non-melanoma skin cancers with 500 mg/m^2/day eflornithine for 4-5 years. One patient was reported to have subclinical ototoxicity in that study. Long-term follow-up of these patients found no increase in adverse events in the treatment group compared to placebo.

CPP FAP-310 will evaluate the eflornithine-sulindac combination in patients with FAP. These patients are at elevated risk for intestinal and colorectal polyposis and other events related to the fact that they harbor germline mutations in the adenomatous polyposis coli (APC) tumor suppressor gene. These genotypic FAP patients express higher levels of the eflornithine target gene, ornithine decarboxylase (ODC) and polyamine contents in apparently normal rectal mucosa than do non-genotypic familial controls. These levels are higher than those reported for patients with sporadic risk of colorectal cancer.

This study will use three (3) 250 mg eflornithine tablets daily in CPP FAP-310. This is based on both safety and efficacy considerations. Both the Lynch study (in FAP patients) and the Bailey study and others (in non-FAP patients) indicate safety of this eflornithine dose. [ENREF 33](#) The Lynch study provides evidence for efficacy of the higher eflornithine dose in FAP patients.

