The eflornithine dose used in the Meyskens 2008 trial of patients with sporadic risk of colorectal cancer was 500 mgs orally per day for three years in combination with 150 mg daily sulindac. No difference in ototoxicity was observed between NSAID alone and combination eflornithine NSAID arms in the Lynch trial of FAP patients, using an eflornithine dose of 750 mgs oral daily. Bailey and colleagues have recently updated their study of patients with prior non-melanoma skin cancer that were treated with 500 mg/m^2 (also rounded to the nearest 250 mg as they used eflornithine tablets) for 4-5 years. The Bailey study demonstrated a significant ( $P < 0.05$ ) increase in uniformly transient audiometric (but not clinically detectable) hearing loss in participants on eflornithine. The follow-up study did not report any clinically significant differences in hearing as compared to the placebo group.

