#### 5.1.1. Eflornithine Clinical Pharmacology

Eflornithine hydrochloride is a member of the following drug classes: 1) inhibitor of ornithine decarboxylase (ODC), 2) hirsutism (excess hair growth) retardant, and 3) antiprotozoals. Eflornithine is FDA approved as a cream for treatment of female hirsutism, and in intravenous form for treatment of trypanosomiasis. The oral tablet form is not available outside of the clinical trial setting in the US and EU. 

**Contraindications:** Prior hypersensitivity to eflornithine. Precaution in patients with bone marrow suppression or hematologic disorders.

**Common side effects:** Low platelet count was dose-limiting after administration of intravenous eflornithine at high doses (up to 3 gm/m^2 every 6 hours for 28 days). Gastrointestinal upset (nausea, vomiting [5%], diarrhea [38%]) have also been reported after these high doses of eflornithine. The primary side effect of low doses of eflornithine (750 mg per day for 3-5 years) is mild ototoxicity with 45.2% of eflornithine subjects versus 33.6% of placebo subjects having a

≥15 dB hearing loss at two adjacent frequencies (p=0.07). The observed audiometric abnormalities were usually reversible; 19% and 18% of eflornithine and placebo subjects had persistent abnormal audiograms 6 months after stopping study drug.

**Infrequent side effects:** Hearing loss/change by audiometry testing has been reported in 8.4% of patients on high dose eflornithine. Rash and alopecia have been reported in 3% of patients. Anorexia and abdominal pain have been reported in 2% of patients treated with eflornithine.

Rare but serious side effects include dizziness (1%), headaches (2%), and seizures (8%) have been reported in patients on intravenous eflornithine. Myelosuppression (including leukopenia, [37%], anemia [55%], and thrombocytopenia [14%]) has been reported at high intravenous doses, but does not usually occur at the low dose (750 mg) utilized in this study.

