### **8.2.11. Treatment Extension Follow-Up (30-days post end of treatment visit +/- 1 week)**

#### **Off Study**

Thirty-days (30) after completion of the treatment extension evaluations, subjects will be contacted by phone for a clinical update in regard to symptoms and interval medical history. Concomitant medications and adverse events will also be reviewed. The subject will provide a clinical update and procedure date for any FAP-related surgical event or major endoscopic excisional event that has occurred since the last contact. These include partial colectomy, colectomy with IRA, total procto-colectomy, proctectomy, pouch resection, sub-mucosal resection, trans-duodenal excision, ampullectomy, duodenectomy, or Whipple procedure.

An FAP-related event at any disease site (colon/rectum/pouch, duodenum) will lead to discontinuation of the study treatment but follow-up of the subject will continue until the end of the 30 day follow-up period.

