- Cardiovascular events include cardiac arrest, cardiac-chest pain, myocardial infarction, thromboembolic event, phlebitis (deep or superficial), and spontaneous abdominal wall or retroperitoneal hematoma at least 10 cm in maximum dimension.
- Grade  $\geq$  3 Cardiac ischemia/infarction or cerebrovascular ischemia, whether related to study drug or not.

Adverse events and serious adverse events must be recorded carefully and completely on the case report forms and SAE report forms. Adverse event reporting and grading will be done using the NCI Common Terminology Criteria for Adverse Events (CTCAE), Version 4.03.

If a subject comes off study treatment for any of the above listed FAP or SAE events, the subject will need to complete all tests, procedures and assessments required at the Final Intervention/End of Treatment visit, including 30-day follow-up.

All subjects who go off study treatment due to an FAP-related event, toxicity, or intercurrent illness, or who withdraw consent for further treatment will be followed for at least 30 days from their last dose of study medication.

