#### **11.4. Safety Parameters**

Subjects will be followed for safety from the start of treatment through 30 days after treatment discontinuation. Serious adverse events will be followed until resolved or returned to baseline, even if longer than 30 days from the subject's off study treatment or off study date.

Adverse events and serious adverse events must be recorded carefully and completely on the case report forms and SAE report forms. Adverse event reporting and grading will be done using the NCI Common Terminology Criteria for Adverse Events (CTCAE), Version 4.03, ([http://evs.nci.nih.gov/ftp1/CTCAE/CTCAE\\_4.03\\_2010-06-14\\_QuickReference\\_5x7.pdf](http://evs.nci.nih.gov/ftp1/CTCAE/CTCAE_4.03_2010-06-14_QuickReference_5x7.pdf)).

Serious adverse events must be reported to the Institutional Review Board (IRB)/Independent Ethics Review Committee (IEC)/Research Ethics Board (REB) by the Investigator and to regulatory authorities (FDA, National Health Authorities) by the Sponsor, according to established policy and regulatory requirements. Adverse events will also be coded to an organ system class. Summaries of safety data will be completed for the study population.

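### The only scheduled adverse-event call after treatment is timed from the end-of-treatment visit, so it can fall on day 23 of a window that runs to day 30 after the last dose

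*Protocol*

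**What the plan says.** **The call.** Protocol 8.2.7 sets the post-treatment contact at "30-days post end of treatment visit +/- 1 week" and states: "Thirty-days (30) after completion of the end of study evaluations, subjects will be contacted by phone". Section 8.2.11 does the same for the extension: "Thirty-days (30) after completion of the treatment extension evaluations, subjects will be contacted by phone". Both calls review adverse events. The monthly calls for months 2 to 6 in 8.2.8 do not add to this. They cover only subjects who stopped for progression with a procedure still pending, they collect procedure dates, and the extension has no counterpart.

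**The visit.** Section 8.2.6, Table 3 footnote 21 and Table 4 footnote 17 place the end-of-treatment visit within two weeks after treatment stops. The heading of 8.2.10 gives two weeks in either direction.

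**The adverse-event window.** Section 11.4 states: "Subjects will be followed for safety from the start of treatment through 30 days after treatment discontinuation". Section 11.7 ends adverse-event documentation at the same point and equates the off-treatment date with the last dose. Protocol 12.6.3 and SAP 5.5.5 count treatment-emergent events to day 30 after the last dose. Section 8.2.14 adds that subjects who stop for an FAP-related event, toxicity, intercurrent illness or withdrawn consent for treatment "will be followed for at least 30 days from their last dose of study medication".

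**Hearing background.** Three sections cite the same skin-cancer prevention study. Section 2.5 says "One patient was reported to have subclinical ototoxicity in that study". Section 2.7.2 reports a significant "increase in uniformly transient audiometric (but not clinically detectable) hearing loss in participants on eflornithine". Section 5.1.1 says "19% and 18% of eflornithine and placebo subjects had persistent abnormal audiograms 6 months after stopping study drug".

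**The concern.** The call and the window it serves start from different days. The window starts at the last dose, and the call is counted from a visit that may be on that day or up to two weeks later. A site that follows 8.2.7 or 8.2.11 exactly can therefore make its last enquiry before the window closes, and for some subjects before the minimum follow-up in 8.2.14 is met. At stake is even ascertainment of non-serious events in the last days of the treatment-emergent period. The primary efficacy analysis is not affected.

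The hearing passages matter less. They are background text, but 2.5 uses the cited study, with others, to support the safety of the eflornithine dose, and a reader cannot tell which description to rely on.

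**Working it through.** The plan states no figure to reproduce here; the check is calendar arithmetic on its own rules.

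**Inputs**
- Visit day after last dose, V: 0 to 14 (8.2.6; Table 3 footnote 21; Table 4 footnote 17).
- Call day after the visit: 30 ± 7, so 23 to 37 (8.2.7, 8.2.11).
- End of adverse-event window: day 30 after last dose (11.4, 11.7, 12.6.3; SAP 5.5.5).

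**Range of the call.** Call day after last dose = V + 30 ± 7.
- Earliest: 0 + 23 = day 23.
- Latest: 14 + 37 = day 51.
- At the nominal 30 days: day 30 (V = 0) to day 44 (V = 14).

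**Days without a scheduled prompt.** These are 30 minus the call day, when positive. The worst case is 30 − 23 = 7 days (days 24 to 30), or 7/30 = 23% of one subject's post-treatment window.

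**When it can happen.** The earliest call is V + 23, which is below 30 only if V < 7. With the visit on day 7 or later, every permitted call is on day 30 or later.

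**How often.** The documents do not give the distribution of visit or call days. Two assumptions give a range:
- All whole-day pairs equally likely: 15 visit days × 15 call days = 225 pairs. Those before day 30 number 7 + 6 + 5 + 4 + 3 + 2 + 1 = 28, and 28/225 = 12%.
- Visit always on the day of last dose: 7 of the 15 permitted call days (23 to 29) fall early, 7/15 = 47%.

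**The 8.2.10 heading.** If its two weeks either way let the visit precede the last dose by 14 days, the earliest call is −14 + 23 = day 9. On equal weighting, 210 of 29 × 15 = 435 pairs (48%) then fall before day 30. The section's text and Table 4 footnote 17 point to a visit around or after stopping, so this shows only why the heading needs reconciling.

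**Hearing passages side by side** (same reference)
- 2.5: one patient with subclinical ototoxicity, in a study described as 291 patients.
- 2.7.2: a significant (P < 0.05) audiometric increase, described as transient in all cases.
- 5.1.1: a shift of at least 15 dB at two adjacent frequencies in 45.2% versus 33.6% on placebo, p = 0.07, with 19% versus 18% persistently abnormal at 6 months.

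The two significance statements differ, a uniformly transient effect does not sit with persistence at 6 months, and one case does not sit with 45.2%. No section says whether the measures differ, and 5.1.1 gives no denominators.

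**The case against.** The strongest reply is that the protocol already contains the 30-day rule. Closing follow-up on day 23 would breach 8.2.14 for the groups it names, and 11.4 and 11.7 set 30 days for everyone. Section 11.7 tells subjects to report any symptom, requires serious events to be reported through day 30, and later if attributable to treatment, and has them followed to resolution. The nominal call is on day 30 or later, and day 23 is an extreme. All of this stands. It means that the late days lack a scheduled prompt, not that events in them are lost. It does not remove the conflict, because a day-23 call satisfies 8.2.7 while falling short of the other sections.

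A reader might infer that 23% of post-treatment safety data go missing. The documents do not support that; 7 of 30 days is one subject's worst case.

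A reader might also infer that follow-up ends too early to judge hearing recovery, because the cited results are at 6 months. The documents do not make this a defect. Persistence in 5.1.1 was nearly equal on placebo (18% against 19%) and has no denominator to apply to this trial. Section 8.2.14 lists tinnitus and hearing-impairment grades among potential serious events, which are followed to resolution if handled as such. Extra phone calls could not replace audiograms. How long to follow hearing is a design choice.

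On the hearing passages, different measures may explain part of the discrepancy, and 2.5 also relies on a combination trial in FAP and other studies. That limits the point to a request for clarification.

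**Conclusion.** The point holds as a scheduling inconsistency. A call made within its stated window can fall on day 23 to day 51 after the last dose, against an adverse-event window ending on day 30. At most 7 days lack a scheduled prompt, and only when the visit is less than 7 days after the last dose. This takes the visit to fall on or after the last dose. The share of subjects affected is unknown; 12% and 47% are illustrations under the two stated assumptions. The consequence is limited to non-serious events that a subject does not volunteer.

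The hearing descriptions are inconsistent as written and should be reconciled. They do not by themselves show that the dose rationale is wrong.

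**What to change.** - In 8.2.7, 8.2.11 and the follow-up columns of Tables 3 and 4, time the call from the last dose, with a window opening no earlier than day 30. The two-week width can stay, for example days 30 to 44. Have the call ask about events through day 30.
- Reconcile the window in the 8.2.10 heading with that section's text and Table 4 footnote 17, so that the visit has one stated relation to the last dose. Check that 8.2.14, 11.4 and 11.7 then agree.
- In 2.5, 2.7.2 and 5.1.1, give one account of the cited study's hearing results, stating the measure, comparator and denominator.
- For subjects already called, list the interval from last dose to call and report how many were below 30 days.

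The SAP definition needs no change, since it already counts from the last dose. The cost is wording in an amendment, with the approvals that Protocol 13.4 requires, and a call up to about a week later for some subjects. Until then, sites could use only the later half of the present window: with a visit on or after the last dose, a call 30 to 37 days after it always falls on day 30 or later and stays within the current text.

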#### **8.2.8. Initial 24 Month Treatment Intervention Follow-Up (Months 2-6, each month +/- 1 week) Off Study**

For the next 5 months after the 30 day follow-up, if the subject went off study treatment for disease progression indicating the need for an any FAP-related surgical event or major endoscopic excisional event, and the surgical/endoscopic event had not yet occurred at the time of the 30 days post end of treatment visit, subjects will be contacted by phone to obtain the procedure date of any FAP-related surgical event or major endoscopic excisional event that has occurred since the last contact. These include partial colectomy, colectomy with IRA, total

procto-colectomy, proctectomy, pouch resection, sub-mucosal resection, trans-duodenal excision, ampullectomy, duodenectomy, or Whipple procedure.

### **8.2.9. Treatment Extension Intervention (Months 25 - 48)**

Subjects completing the initial 24 months of study treatment, without an FAP related event, and have completed all the 24 month visit procedures as outlined in Section 8.2.6 and Table 3 and Table 4 may be eligible to participate in the treatment extension.

In order to participate, a subject must meet the following requirements:

1. Subject has completed 24 months of treatment without an FAP related event.
2. Subject has completed all the month 24 visit procedures.
3. Subject is no more than 14 days beyond the 24 month or 36 month visit.
4. Subject has signed the informed consent for treatment extension.

Once the above requirements are met, the subject will have drug and diary dispensed.

At months 25, 26, 28, 29, 31, 32, 34, 35, 37, 38, 40, 41, 43, 44, 46, and 47 ( $\pm$  1 week), a follow-up visit via phone contact to assess for side effects, other medications, to remind subjects to complete their diary and to continue to take their study medications.

At the 27-month, 33-month, 39-month and 45-month visits ( $\pm$  1 week), subjects will have drug and diary dispensing. Women of child bearing potential will also have a serum pregnancy test performed. Concomitant medications, adverse events and medication compliance will also be reviewed.

At the 30-month and 42-month visits ( $\pm$  2 weeks), subjects will have a physical exam/review of body systems (including weight and vital signs), blood samples obtained for laboratory tests (CBC, chemistry panel, urinalysis), a random urine sample will be obtained for polyamine determination, EKG (Subject needs to be in the supine position for 10 minutes prior to the EKG) and their first on study treatment upper and lower endoscopy procedures. A normal rectal/pouch mucosal biopsy for polyamine determination will be obtained during the colonoscopy/proctoscopy procedure. Women of child bearing potential will also have a serum pregnancy test performed. Concomitant medications, adverse events and medication compliance will also be reviewed. Quality of life questionnaires (EORTC QLQ-C30, EORTC QLQ-CR29, EQ-5D, and the modified Cancer Worry Scale) will be provided to the subject to complete.

At the 36-month, and 48-month visits ( $\pm$  2 weeks), subjects will have a physical exam/review of body systems (including, weight and vital signs), blood samples obtained for laboratory tests (CBC, chemistry panel, urinalysis), a random urine sample will be obtained for polyamine determination, audiometry testing, EKG (Subject needs to be in the supine position for 10 minutes prior to the EKG) and their second set of on study treatment endoscopy procedures. A normal mucosal biopsy for polyamine determination will be obtained during the colonoscopy/proctoscopy procedure. Study drug and diaries will be dispensed at 36-month if eligible to continue. Women of child bearing potential will also have a serum pregnancy test performed. Concomitant medications, adverse events and medication compliance will also be reviewed. Quality of life questionnaires (EORTC QLQ-C30, EORTC QLQ-CR29, EQ-5D, and the modified Cancer Worry Scale) will be provided to the subject to complete. A food frequency questionnaire will be provided to the subject to complete at North American (United States and Canada) sites only.

